8.3.1.2 Event-free Survival at 12 Months

Event-free survival will be evaluated using the time in months from transplant to either the first event or their last evaluation calculated as:

12*(date of event/last evaluation – date of transplant)/365.25,

or, for HSCT control subjects for whom the dates were not recorded, as:

age in months at death/end of follow-up - age in months at transplant.

For the purpose of this analysis, the events of interest are:

- death:
- reinstitution of PEG-ADA ERT;
- requirement for a second transplant.

Event-free survival will be summarized in the same way as overall survival described in Section 8.3.1.1.

Final Version 4.0 Page 18 of 27

In addition, if there are any events (other than death), the time to each event will be summarized in a similar manner to the overall event-free survival.

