4.2.1.2 Evaluation of Efficacy

Primary Efficacy: Overall/event-free survival (survival without need for BMT or PEG-ADA).

Overall/event-free survival will be determined for each subject by 12 months where failure is defined by one of the following endpoints: death; reinstatement of PEG-ADA; or performance of an allogeneic BMT.

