6.4 Precautionary and Prohibited Medications and Procedures

6.4.1 Prohibited Medications and Procedures

Criteria for PEG-ADA administration

PEG-ADA will be continued through marrow harvest, conditioning and cell product infusion. PEG-ADA will be stopped on day +30 post cell product infusion if the patient received busulfan and the final cell product, and does not have active infections or other major medical problems.

We will recommend restarting PEG-ADA if:

By 12 months after the cell product infusion there is any one of the following:

- a) no evidence of PBMC or erythrocyte ADA enzyme activity above baseline/pre-treatment level,
- b) no evidence of immune reconstitution (absolute # CD3 cells <200/mm³),
- c) no detectable gene-marked granulocytes by ddPCR/qPCR (<1/10,000 cells).

The patient will be put back on PEG-ADA, and be followed-up medically.

PEG-ADA **may** be re-started if:

The PI deems it in the best interest of the subject on clinical grounds e.g. multiple, serious or unresponsive infections or sub-normal immune reconstitution.

PEG-ADA **may** be re-stopped (after it has been re-started for above reasons) if:

Criteria for being off are present: no active infections, PBMC or erythrocyte ADA >baseline/pre-treatment levels, absolute CD3+ T cells counts $\geq 200/\text{mm}^3$, and peripheral blood samples are positive for vector sequences by ddPCR/qPCR.

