8.4 Follow-up

Following the infusion of the gene-modified cells, the subjects will be evaluated and the following exams will be performed (if sufficient samples can be obtained):

Day +1

1. Physical Exam
2. Safety/toxicity studies:
 - a) CBC with differential
 - b) Serum chemistry panel, electrolytes

Months 1, 2, 3, 4, 5, 6, 8, 10, 12, 15, 18, 21, and 24

1. Physical Exam
2. Safety/toxicity studies:
 - a) CBC with differential
 - b) Serum chemistry panel, electrolytes
 - c) PBMC to be analyzed at 3, 6, 12 and 24 months by PCR for RCL and archived annually, thereafter.
 - d) Serum to be banked at 3, 6, 12 and 24 months and annually thereafter, for possible western blot testing for RCR.
 - e) Monitoring for leukemia (by LAM-PCR) at approximately 6-month intervals for the first five years post-infusion, then annually for an additional 10 years (15-year total monitoring after infusion) if criteria for triggering LAM-PCR are fulfilled (see monitoring plan).
3. Efficacy
 - a) Measurements of leukocyte ADA enzymatic activity and deoxyadenosine metabolites in RBC
 - b) Immune function testing

- i) Determination of absolute numbers of CD3+, CD4+ and CD8+ T lymphocytes CD19+ B lymphocytes and CD56/CD16+ NK cells
 - ii) Proliferative responses to PHA, tetanus toxoid.
 - iii) Measurement of serum immunoglobulin levels (IgG, IgA, IgM) (Q 3 months if not receiving IVIg)
 - iv) Measurement of specific antibodies to tetanus toxoid and phosphoribosyl phosphate
 - v) TREC
 - vi) TCR V β Usage
4. Gene transduction/expression:
- a) Measurement of the frequency of cells containing the inserted ADA gene in PBMC and granulocytes as well as FACS-sorted T cells and myeloid cells by PCR
 - b) Measurement of ADA expression in leukocytes by ADA enzymatic assay and possibly RT PCR (if samples are positive by DNA-PCR)
 - c) Vector integration site analysis

The allowable window for the follow-up exams/tests is \pm 4 weeks.

After the 24 month time-point, subjects will be enrolled into a separate long-term follow-up protocol, in which they will be followed once every six months for an additional 3 years, and then once per year, for an additional 10 years. The total time that they will be followed after treatment is 15 years (see monitoring plan described in [Appendix F](#)).

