5.1 Primary Endpoints

The primary endpoints are:

- Safety: the incidence and severity of serious adverse events (SAEs)
- Efficacy: overall and event-free survival at 12 months, where events are death, reinstitution of PEG-ADA therapy and performance of an allogeneic BMT.

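### A PEG-ADA restart decided at the month-12 visit can be dated after 12.0 months and scored event-free at 12 months

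*SAP*

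**What the plan says.** The primary efficacy endpoint in SAP 5.1 is "overall and event-free survival at 12 months, where events are death, reinstitution of PEG-ADA therapy and performance of an allogeneic BMT". Protocol 4.2.1.2 sets the same horizon: "Overall/event-free survival will be determined for each subject by 12 months where failure is defined by one of the following endpoints".

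SAP 8.3.1.2 supplies the clock. "Event-free survival will be evaluated using the time in months from transplant to either the first event or their last evaluation", computed as "12*(date of event/last evaluation – date of transplant)/365.25". The PEG-ADA event is "reinstitution of PEG-ADA ERT": the restart itself, not the finding that led to it. The outputs follow SAP 8.3.1.1: the proportion at 12 months, a Kaplan-Meier curve with its 12-month estimate, and a Beta(1,1) Bayesian analysis.

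The protocol says in several places when PEG-ADA is restarted:

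- Section 6.4.1: "We will recommend restarting PEG-ADA if", then "By 12 months after the cell product infusion there is any one of the following": no ADA activity above baseline, CD3 below 200, or no marked granulocytes (below 1/10,000). It also lets the investigator restart on clinical grounds, with no time limit.
- Section 7.5: a mandatory restart at 6 months when ADA activity, immune reconstitution and marking (below 1/100,000) are all absent. The three conditions are joined by an and.
- Appendix B refers the reader to 6.4.1 for PEG-ADA management.

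Section 8.4 adds the visit tolerance: "The allowable window for the follow-up exams/tests is" plus or minus 4 weeks.

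**The concern.** The 6.4.1 deadline and the EvFS landmark are the same time point, but the first concerns a finding and the second an act that follows it. A child whose failure is settled on month-12 data, and who is restarted exactly as 6.4.1 recommends, may have a restart date just past 12.0 months. The SAP would then count that child as event-free in the 12-month proportion, the Bayesian number of successes and the 12-month Kaplan-Meier estimate. Neither document says how this child is to be counted.

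Section 7.5 does not close the gap. A child with, for example, CD3 below 200 but detectable marking fails one 6.4.1 criterion and does not meet the 6-month rule. So does a child whose marking lies between the two thresholds and who fails no other criterion.

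Within the OTL-101 group such a slip can only raise 12-month EvFS. With 20 children, one is enough to change the headline.

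**Working it through.** **The plan's own figure.** Protocol 11.4 gives precision, as the half-width of a two-sided exact 95% CI, of 12% for one failure in 20 and 7% for none.

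- 19/20: Clopper-Pearson 75.1% to 99.9%; half-width (99.87 − 75.13)/2 = 12.4%. This reproduces 12%.
- 20/20: lower limit 0.025^(1/20) = 83.2%; half-width (100 − 83.2)/2 = 8.4%. The stated 7% appears only with all 5% in the lower tail: 0.05^(1/20) = 86.1%, half-width 6.96%. This is a side point. The two-sided intervals are used below.

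**When a restart can be dated.** Inputs: 12.0 months = 365.25 days (SAP formula), so one month is 30.44 days; window ±28 days (Protocol 8.4). Two assumptions are not in the documents: the visit date is uniform over its window, and a lag L of 0 to 28 days separates visit from restart. The only turnaround given, in Protocol 14.2, is 2 to 3 weeks for a different assay.

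- Restart under the 6-month rule: latest date (182.6 + 28 + L)/30.44 = 6.9 to 7.8 months. None is missed at 12.0.
- Restart under 6.4.1 on month-10 data: latest date (304.4 + 28 + L)/30.44 = 10.9 to 11.8 months. None is missed.
- Restart under 6.4.1 on month-12 data: date = 365.25 + U + L, with U uniform on (−28, 28). P(date > 365.25) = (28 + L)/56.

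| Lag L (days) | P(restart after 12.0 months) | Range of restart (months) |
|---|---|---|
| 0 | 28/56 = 50% | 11.1–12.9 |
| 7 | 35/56 = 62.5% | 11.3–13.1 |
| 14 | 42/56 = 75% | 11.5–13.4 |
| 21 | 49/56 = 87.5% | 11.8–13.6 |
| 28 | 56/56 = 100% | 12.0–13.8 |

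These probabilities apply only to a child first acted on at the month-12 visit.

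**Effect of one such child**, if the other 19 are event-free.

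- Counted as a failure: 19/20 = 95% (75.1–99.9%); posterior mean (1 + 19)/(2 + 20) = 20/22 = 90.9%.
- Counted as event-free: 20/20 = 100% (83.2–100%); posterior mean 21/22 = 95.5%.
- Against a purely illustrative control of 12/20, the SAP's posterior probability that OTL-101 is better moves from 0.996 to 0.999.

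**What a later cut would catch.** With the cut at 12 months + 4 weeks, P(restart still later) = P(U > 28 − L) = L/56: 0% with no lag, 25% at 14 days, 50% at 28 days. A later cut alone is therefore not complete unless the lag is zero.

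**The case against.** The strongest reply has five parts.

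1. A reader might infer that a complete non-responder is usually counted as a 12-month success. The documents do not support this. A child with no ADA activity, no reconstitution and no marking meets the 6-month rule in Section 7.5 and would be dated by about month 8 at the latest. This objection stands in full. That child would be exposed only at a site following 6.4.1 alone, to which Appendix B points.
2. By 12 months can be read as an outer limit. The investigator may restart sooner, and ADA activity, lymphocyte subsets and marking are scheduled at months 6, 8 and 10. This stands, and limits the gap to children first acted on at month 12.
3. A late restart is not lost. Once the data are available it enters the full Kaplan-Meier curve, the separate time-to-each-event summary and 24-month EvFS. Individual plots of CD3, marking and ADA activity would also show it. This stands, but these do not correct the three 12-month outputs that carry the primary endpoint.
4. Control events are acts too (a return to PEG-ADA or a second transplant), and they may also follow graft failure by weeks. This stands: nothing in the documents shows that control failures are counted any sooner.
5. A date-based landmark is unambiguous, and the protocol's background section reports 100% EvFS in 18 evaluable patients at the March 2016 cut-off. Follow-up was then partial, so this does not exclude a later case, but it gives no sign that such cases are common.

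What remains is a narrow group for which the plan has no counting rule or sensitivity analysis.

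**Conclusion.** The point holds in limited form. A child who fails one or two 6.4.1 criteria, is not restarted earlier and is restarted on month-12 data can be scored event-free at 12 months. The chance for such a child is 50% to 100% as the lag runs from 0 to 28 days. Both the uniform visit date and the lag are assumptions, and the documents do not say how many such children to expect. One of them moves the exact lower limit from 75.1% to 83.2%.

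Two larger conclusions might be drawn and should not be. The endpoint does not lose its ability to detect failure at its landmark, because a child with no effect on any measure falls under the 6-month rule. Nor do the documents establish that the comparison with HSCT controls favours OTL-101. Only the within-group direction is certain. This is a cheap improvement to the SAP, not a flaw that invalidates the primary analysis.

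**What to change.** Keep the date-based analysis at 12.0 months as the main one. Add to SAP 8.3.1.2:

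- A pre-specified sensitivity analysis that repeats the 12-month EvFS proportion, Bayesian and Kaplan-Meier estimates with the cut at 12 months + 4 weeks. It counts every death, PEG-ADA restart and second transplant up to that date, in OTL-101 and HSCT controls alike, whatever the trigger. Counting one group by trigger and the other by date would create a new imbalance.
- A listing of OTL-101 children who meet a 6.4.1 criterion on month-12 data and have no restart dated by that cut, with 12-month EvFS shown again counting them as failures. This picks up the restarts that a lag pushes beyond the later cut. It is descriptive and for one group only, since controls have no month-12 protocol visit.

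The cost is a few sentences and a little more analysis of data already collected. EvFS in each group can only stay the same or fall slightly; the difference between groups could move either way. Controls with only ages in months may not resolve a 4-week shift, and the SAP should say how they are handled.

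Separately, Protocol 6.4.1 and 7.5 must be reconciled. They differ on timing (12 against 6 months), on criteria (any one against all three), on the marking threshold (1/10,000 against 1/100,000) and on force (a recommendation against a requirement). The PEG-ADA component of EvFS depends on which is followed. No clinical rule is proposed here.

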This is a retrospective, non-interventional data collection activity; the patients follow routine medical practice. We will contact GOSH patients or their authorised representative and seek their consent to get access to their medical notes and share the information with regulatory agencies and pharmaceutical companies. Teams at GOSH/UCL and Duke University Children's Hospital will work on the collection of data from databases and patients' records, and the data will be entered into an electronic Case Report Form (eCRF). This eCRF will be monitored as per standard process before it can be used for statistical analysis and submission to agencies for review and assessment.

6. Data Analysis

The comparison analysis between gene therapy and HSCT will be done based on the current gene therapy study objective:

Survival and event free survival, defined as need to return to PEG-ADA or second transplant at 1 and 2 years post treatment.

Use of immunoglobulin replacement therapy (IgRT) and severe infections post treatment.

Severe infections, defined as infections requiring hospitalisation or prolonging hospitalization and/or documented infections by opportunistic pathogens (interstitial pneumonia, intractable diarrhoea)

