8.3 Efficacy Evaluations

The primary comparison for all efficacy analyses will be between the OTL-101 treated subjects and the allogeneic HSCT controls treated at either GOSH or Duke University without a matched related donor.

Secondary comparisons will be between:

- the OTL-101 treated subjects and the HSCT controls treated at either GOSH or Duke University with a matched related donor;
- the OTL-101 treated subjects and the total group of HSCT controls.

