8.3.2 Secondary Efficacy Endpoints

8.3.2.1 Overall and Event-free Survival at 24 Months

Overall and event-free survival at 24 months will be summarized in the same way as for the analyses at 12 months described in Sections 8.3.1.1 and 8.3.1.2.

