8.3.2.2 Use of Immunoglobulin Replacement Therapy

The number (%) of subjects receiving immunoglobulin replacement therapy (IgRT) will be summarised by visit for the OTL-101 treated subjects.

The time to cessation of IgRT will be calculated (in months) as:

12*(stopping date of IgRT – date of transplant) /365.25,

or, for HSCT control subjects for whom the dates were not recorded, as:

age in months when IgRT stopped – age in months at transplant.

Time to cessation of IgRT will be summarised for the OTL-101 treated and HSCT control groups using descriptive statistics and, if appropriate, estimated from a Kaplan-Meier curve in which subjects who are still receiving IgRT will be censored at the time of their last visit.

The number (%) of subjects who have stopped treatment with IgRT at 12, 18 and 24 months without restarting at any subsequent time point will be summarized for the OTL-101 treated and HSCT control groups (data permitting).

In addition, serum immunoglobulin levels (IgG, IgA and IgM) will be measured at each visit for the OTL-101 treated subjects. Levels of IgG, IgA and IgM and changes from baseline will be summarised by visit using descriptive statistics. In addition, plots of the median value and range over time on a logarithmic scale will be produced for each parameter along with individual plots for each subject which will include age-dependent normal ranges provided by the study sites.

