8.3.3 Additional Efficacy Endpoints

8.3.3.1 Use of PEG-ADA Enzyme Replacement Therapy

The time to withdrawal of PEG-ADA ERT will be calculated (in months) as: 12*(stop date of PEG-ADA ERT – date of transplant) /365.25, or, for HSCT control subjects for whom the dates were not recorded, as: age in months when PEG-ADA stopped – age in months at transplant.

Time to withdrawal of PEG-ADA ERT will be summarised for the OTL-101 treated and HSCT control groups using descriptive statistics and, if appropriate, estimated from a Kaplan-Meier curve in which subjects who are still receiving PEG-ADA ERT will be censored at the time of their last visit.

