10.2 Changes in Version 4.0

Since version 3.0 of the Statistical Analysis Plan was signed off, the sponsor has received regulatory approval to include further HSCT control data from Duke University, so this SAP has been updated to include these data.

The following additional changes have been made:

- Details added to clarify the calculation of time to event for subjects in the HSCT control group who do not have the dates of events recorded.
- Tables of reference ranges have been deleted to allow the most up to date ranges received from the study sites to be used in the analyses.
- The summary of coagulation data has been moved from the safety section to the baseline section as these data are only collected prior to the transplant.
- The MedDRA version to be used has been updated to 20.0.

Final Version 4.0 Page 27 of 27

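### For HSCT controls without recorded dates, the SAP times event-free survival with the overall survival formula, so non-fatal failures are not timed

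*SAP*

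**What the plan says.** SAP 8.3.1.2 measures event-free survival as the "time in months from transplant to either the first event or their last evaluation". It lists three events: death, PEG-ADA restart and second transplant. The formula for subjects with dates runs to the date of the event. For HSCT controls without recorded dates the fallback is "age in months at death/end of follow-up - age in months at transplant". The identical line serves overall survival in SAP 8.3.1.1.

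SAP 8.3.2.1 says that both outcomes at 24 months "will be summarized in the same way as for the analyses at 12 months". SAP 10.2 explains that version 4.0 clarified the "calculation of time to event for subjects in the HSCT control group who do not have the dates of events recorded".

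Two neighbouring fallbacks for undated controls are built on the event itself: SAP 8.3.2.2 starts from "age in months when IgRT stopped" and SAP 8.3.3.1 from "age in months when PEG-ADA stopped". Protocol Appendix H, part 6, describes the endpoint for the comparison with HSCT as "event free survival, defined as need to return to PEG-ADA or second transplant at 1 and 2 years post treatment". On the comparator, SAP 8.3 states: "The primary comparison for all efficacy analyses will be between the OTL-101 treated subjects and the allogeneic HSCT controls", meaning those at the two named hospitals without a matched related donor.

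**The concern.** The definition and the fallback in SAP 8.3.1.2 cannot both be followed for an undated control whose first event is not death. The definition stops the clock at the PEG-ADA restart or second transplant. The fallback lets it run to death or the end of follow-up. The two events it leaves out are the two by which Appendix H describes the endpoint. No other section gives an event-free survival formula for undated controls.

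Event-free survival at 12 months is a primary efficacy endpoint, and the contrast with controls lacking a matched related donor is the primary comparison. SAP 8.3.1.2 applies all the overall survival methods to it: proportion with exact interval, Kaplan-Meier, log-rank and Bayesian. The OTL-101 estimate is untouched. If an affected control exists, the control Kaplan-Meier curve is wrong, and so is any proportion, Bayesian count or log-rank test derived from that time.

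Non-fatal failure is plausible in this comparator. Protocol Table 1 shows 14 of 19 haploidentical recipients at Duke alive but only 7 alive with T-cell engraftment. That is background only: non-engraftment is not itself a listed event, and overlap with the 2000-2016 controls is not stated.

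**Working it through.** The plan states no figure for this quantity, so there is none to reproduce. The check puts example histories through the two rules and then measures the effect on the planned summaries.

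**Step 1: individual histories.** Assume transplant at age 6 months. The fallback gives (6 + months to death or end of follow-up) - 6; the definition gives (6 + months to first event) - 6.

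| History after transplant | Fallback | Definition | Consequence |
|---|---|---|---|
| Failure at month 6, alive at 60 | 60 | 6 | missed at 12 and 24 |
| Failure at month 18, alive at 60 | 60 | 18 | missed at 24 |
| Failure at month 6, death at 18 | 18 | 6 | missed at 12, counted at 24 |
| Failure at month 6, follow-up ends at 9 | 9 | 6 | event at 9 or status unknown; not event-free at 12 |

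The failure is therefore missed only at a landmark that the follow-up passes.

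**Step 2: how many controls.** Appendix H identifies 25 controls at GOSH and 10 at Duke, 35 in all, of any donor type. The number without a matched related donor, the number undated and the length of follow-up are not given. Duke is a likely source of undated controls because Appendix H lists year of birth and ages there. That is an inference and not a cap: SAP 8.2.1 and 8.2.17 take age and follow-up duration from the eCRF for HSCT controls generally.

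**Step 3: effect per misclassified control, complete follow-up.** The control proportion rises by 1/n: 1/15 = 6.7 points, 1/20 = 5.0, 1/25 = 4.0 (n assumed).

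**Step 4: Kaplan-Meier.** All inputs are assumed: n = 20, deaths at months 3, 5, 7 and 9, PEG-ADA restart at month 6, all others followed to month 60 unless stated. The fallback fixes only the time, so the restart is shown both with its event flag kept and with it dropped (censored).

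- *No other censoring.* Correct: 15/20 = 75.0% at both landmarks. Restart moved to month 60: 16/20 = 80.0% at both. Moved to month 18: 80.0% at 12 months, then 75.0% (kept) or 80.0% (dropped) at 24. Moved to month 10 with the flag kept: 75.0% at both, so no error.
- *Five controls censored at month 15, restart moved to month 18.* Correct: 75.0% at both. As written: 80.0% at 12 months. At 24 months, flag kept: 0.800 × 10/11 = 72.7%; flag dropped: 80.0%.
- *Three controls censored at month 8, restart moved to month 11.* Correct: 16/20 × 12/13 = 73.8%. As written, flag kept: 17/20 × 13/14 × 12/13 = 72.9%; flag dropped: 17/20 × 13/14 = 78.9%. The same values hold at 24 months.

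Across these cases the error is -1.0 to +5.1 points at 12 months and -2.3 to +5.1 at 24 months.

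**Step 5: Bayesian comparison.** SAP 8.3.1.1 uses Beta(1,1) priors. Assume OTL-101 is 20/20, giving a Beta(21,1) posterior, and control n = 20. Then P(OTL-101 > control) = 1 - E[B^21], where B is the control rate with posterior Beta(1 + X, 21 - X).

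- X = 15: 1 - (16·17·18·19·20·21)/(37·38·39·40·41·42) = 0.990
- X = 16: 1 - (17·18·19·20·21)/(38·39·40·41·42) = 0.976
- X = 17: 1 - (18·19·20·21)/(39·40·41·42) = 0.947
- X = 18: 1 - (19·20·21)/(40·41·42) = 0.884

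One misclassified control thus moves the probability from 0.990 to 0.976, or from 0.947 to 0.884. At 20/20 the log-rank test would not be run, because SAP 8.3.1.1 requires at least one event in each group.

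**The case against.** The strongest reply is that the section corrects itself. Its opening sentence, its dated formula and its event list all point to the first event. Its last line asks for the time to each non-fatal event, which cannot be produced for an undated control without timing that event. A sensible programmer would see this. That makes a drafting slip the likely explanation, but the one explicit formula for these controls still says something else, and two programmers could follow the section to different results.

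SAP 8.3.1.1 also does not say that the 12-month proportion or the Bayesian count is computed from the time variable. If status is counted directly, both are unaffected. This stands: the Bayesian figures above hold only if the count is derived from the time, whereas the Kaplan-Meier curve uses the time in any case.

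Much of the timing is planned. Appendix H collects PEG-ADA restart at Duke as time since transplant, and lists transplant and death dates for GOSH. This makes the correction easy, but the fallback does not use the restart time.

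Finally, no posterior threshold is set, the trial was sized on practical grounds, and with complete follow-up the error works against OTL-101. All true. None of it makes a wrong derivation acceptable on a primary endpoint, and under censoring the direction is not assured. Appendix H also cites a single-centre trial title although this study has two centres, so it is secondary support. The contradiction within SAP 8.3.1.2 does not depend on it.

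**Conclusion.** The concern holds. The fallback in SAP 8.3.1.2 is wrong as written: it contradicts the definition in its own section and the pattern of the parallel fallbacks, and it carries over to 24 months. The actual effect is unknown and may be nil, because the documents do not show that any undated control had a non-fatal first event. If one did, was followed past the landmark and all follow-up is complete, control event-free survival is overstated by 1/n, about 4 to 7 points for an assumed n of 25 down to 15. With other controls censored and the event flag kept, it can instead be understated, by 1.0 point at 12 months and 2.3 at 24 months in the cases shown. It should be corrected, although no result is shown to have been altered.

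**What to change.** In SAP 8.3.1.2, replace the fallback for undated HSCT controls with: age in months at first event (death, PEG-ADA reinstitution or second transplant), or at end of follow-up if there was no event, minus age in months at transplant. Where PEG-ADA reinitiation is recorded as time since transplant, as Appendix H plans for Duke, use that time directly. Apply the same rule to the summaries of time to each event and to the 24-month analysis.

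One query goes with this: confirm that the control eCRF, which is not available here, captures when a second transplant took place. Appendix H lists only the need for one. If the timing is not captured, the SAP should state how such a control is handled.

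The cost is one line of SAP text and the matching derivation program.
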